6. DOSAGE AND ADMINISTRATION

The term 'Study Drug' refers to treatment with either imetelstat or placebo.

Subjects may receive study drug until disease progression, unacceptable toxicity, or withdrawal of consent.

Supportive Care

All subjects will receive supportive care (including transfusions or myeloid growth factors) as needed per investigator discretion and according to local standard practices. Should an exceptional situation arise where it is deemed clinically necessary to give a transfusion for a Hb >11 g/dL, the reasons should be documented in the CRF.

Study Drug (Imetelstat or Placebo)

Imetelstat Sodium (GRN163L) for injection (imetelstat) is the investigational product in this study and will be provided by the sponsor.

Placebo will be supplied by the sponsor.

Study drug will be administered as a 2-hour IV infusion (\pm 10 minutes) at a constant rate using an infusion pump.

The baseline weight (ie, body weight determined at Screening) will be used to calculate the dose of study drug to the nearest 0.1 mg. The dose should be recalculated if there is a \geq 10% weight change from baseline. Note that the total dose may be recalculated more frequently (eg, at each study visit) depending on local practice. Study drug will be administered IV on a 28-day cycle.

The first dose of study drug should be administered within 72 hours of enrollment (Part 1) or randomization (Part 2) in IWRS.

All subjects in Parts 1 and 2 will receive a starting dose of 7.5 mg/kg of study drug given IV every 4 weeks. Subjects whose dose was previously escalated (before Amendment 2) may continue at the 9.4 mg/kg dose. Study drug dose delay or reduction for Grade 3 or Grade 4 toxicity will be instituted as needed, per the instructions provided in Table 7, Table 8, Table 9, Table 10, and Table 11. Note that these instructions are intended for Grade 3 or Grade 4 toxicities observed at the time of the planned dose on Day 1 of the next cycle. These instructions are not applicable when toxicities occur mid-cycle and subsequently resolve to Grade $<$ 3 by the time of the next planned dose.

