At time 0, just prior to administering the first dose of study drug, collect a set of triplicate 12-lead ECGs, 2 minutes apart.

Administer blinded study drug.

At 0.5 hours after start of infusion (SOI), 1 hour after SOI, immediately before the end of 2-hour infusion, 4, 6, and 8 hours after SOI, collect a set of triplicate ECGs, 2 minutes apart, and 1 blood sample for PK analysis for each time point, respectively.

Blood Volume for the Ventricular Repolarization Substudy**Table 16: Volume of Blood to be Collected from Each Subject in the Ventricular Repolarization Substudy**

Type of Sample	Volume per Sample (mL)	No. of Samples per Subject ^a	Total Volume of Blood (mL) ^b
Safety (including screening and posttreatment assessments)			
- Hematology	5	18	90
- Prothrombin time (PT)/ international normalized ratio (INR) and activated partial thromboplastin time (aPTT)	5	1	5
- Serum EPO level	2	1	4
- Serum chemistry ^c	10	17	170
- B12/folic acid/reticulocytes, serum ferritin (screening), transferrin saturation ^d	5	1	5
- Serum Ferritin (post-screening)	5	12	60
- Hepatitis serologies	13	1	13
- Serum β -hCG pregnancy tests	2	1	2
Pharmacokinetic samples	2	6	12
Approximate Total			361 mL

Note: An indwelling intravenous cannula may be used for blood sample collection.

^a Volumes below derived for median 12 cycle duration and includes end of treatment visit.

^b Calculated as number of samples multiplied by amount of blood per sample.

^c Serum chemistry includes basic liver function tests. An expanded panel of liver function tests may also be required for safety reasons. See Time and Events Schedule above.

^d Total iron binding capacity and serum iron (Fe) may be performed to calculate transferrin saturation if transferrin saturation is not available at the site

Rationale for the Study Design

In accordance with ICH E14 guideline, QT evaluation is now expected to be routine in oncology drug development, and a thorough QT (TQT) study should be conducted, if possible, in healthy subjects.

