Pharmacokinetics data from Study MDS3001 (Part 1) and Study MYF2001 consistently demonstrated a plasma half-life of approximately 4 to 5 hours and no plasma accumulation at later cycles (starting from Cycle 2 Day 1) when imetelstat is given q3w or q4w. The catabolism of the oligonucleotide is expected to produce shorter-length oligonucleotides and thus expected to have similar or shorter half-lives in plasma. Time points for ECG and pharmacokinetic measurements have been selected to match the expected pharmacokinetic profile of imetelstat so that correlations between ECG changes and drug exposure may be appropriately evaluated. In addition, to assess potential delayed QT effects, time-matched PK and ECG samples are collected at later time points when the plasma concentration of imetelstat is expected to be very low. Given these considerations, triplicate ECGs followed by blood samples for pharmacokinetic assessment will be collected at 0.5 and 1 hour post start of infusion, 2 hour (immediately before end of infusion; EOI), 4, 6, and 8 hours after SOI on Cycle 1 Day 1.

To assess the QT interval prior to imetelstat exposure, baseline triplicate ECG assessments will be performed prior to the first study drug administration at three separate time points on Cycle 1 Day 1 (1 hour pre-dose, half hour pre-dose and immediately pre-dose). Because this is a randomized placebo-controlled blinded study design, the inclusion of the placebo data allows for the detection of diurnal variation (Garnett et al 2018^c), baseline triplicate ECG assessment will be collected on Cycle 1 Day 1 at the time points noted previously. Following the hour 0 assessments, time-matched triplicate ECG assessment will be collected at hour 0.5, 1, 2 (immediately before EOI), 4, 6, and 8 on Cycle 1 Day 1. PK samples are to be collected immediately after ECGs.

Based on the known and expected pharmacokinetic properties of imetelstat, the proposed pharmacokinetic and ECG time points on Cycle 1 Day 1 are deemed adequate to characterize the relationship between exposure and effect on QT/QTc.

Sample Size Determination

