The exposure-response relationship will be evaluated using linear model of Δ QTcF as the dependent variable. The data from the study drug and placebo treatment will be included in the model. The drug concentration level will be set to zero for placebo treatment. The independent variables included in the model will be imetelstat plasma concentrations as the explanatory variate (0 for placebo), centered baseline QTcF (i.e., baseline QTcF for individual subject minus the population mean baseline QTcF for all subjects)

as an additional covariate, treatment (active = 1 or placebo = 0), time (i.e., nominal post-dose time point) as fixed effects, and random effects on the intercept and slope per subject (Garnett et al 2018^c).

The key assumptions of the linear mixed-effects model will be absence of hysteresis and linearity of the concentration-response relationship. The linearity of the concentration-response relationship will be evaluated by visual inspection of relevant goodness-of-fit (GOF) plots. If the linear concentration-response relationship model appears to be inappropriate, a non-linear model, such as E_{\max} , log-linear or other sigmoid relationships, will be explored. To detect hysteresis, mean $\Delta\Delta\text{QTcF}$ at each nominal time point will be calculated as the difference between the mean ΔQTcF for study drug minus mean ΔQTcF for placebo. Mean $\Delta\Delta\text{QTcF}$ will be plotted against nominal time to evaluate the nominal time point of maximum response. Absence of hysteresis will be concluded if the time point of maximal effect does not differ from the time of peak plasma concentration (t_{\max}) by more than an hour. If the assumption of absence of hysteresis does not appear to hold, pharmacokinetic-pharmacodynamic models, such as an effect compartment model or an indirect response model, will be explored. If deemed necessary, the concentration- ΔQTc models will be fit for QTc calculated using other appropriate methods.

Criteria for a “QT negative” result

The criterion for a “QT negative” drug is that the upper bound of the 2-sided 90% confidence interval (CI) of the predicted mean $\Delta\Delta\text{QTc}$ is <20 ms at the observed geometric mean C_{\max} at 7.5 mg/kg dose of imetelstat.^{a,b}

^a Rock EP, Finkle J, Fingert HJ, et al. Assessing proarrhythmic potential of drugs when optimal studies are infeasible. *Am Heart J.* 2009;5:827-836.

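### The QTc substudy's hysteresis check has no minimum effect size, so it flags hysteresis by chance in about 67% of trials when there is no QT effect, and the protocol does not say which model then decides.

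*Protocol*

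**What the plan says.** Attachment 11 (Statistical Methods) makes a linear mixed-effects concentration-QTcF model the primary analysis and lists absence of hysteresis among its key assumptions. To check it, the mean placebo-corrected change in QTcF "will be plotted against nominal time to evaluate the nominal time point of maximum response". The decision rule is: "Absence of hysteresis will be concluded if the time point of maximal effect does not differ from the time of peak plasma concentration", with the sentence continuing "by more than an hour. If the assumption of absence of hysteresis does not appear to hold". In that event pharmacokinetic-pharmacodynamic models, "such as an effect compartment model or an indirect response model, will be explored".

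The ECG and PK times are fixed in the same attachment: "At 0.5 hours after start of infusion (SOI), 1 hour after SOI, immediately before the end of 2-hour infusion, 4, 6, and 8 hours". On the dosing side, Section 6 states: "Study drug will be administered as a 2-hour IV infusion", at a constant rate.

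The drug is called QT negative if the upper bound of the two-sided 90% CI for the predicted mean placebo-corrected change is below 20 ms at the geometric mean Cmax. Attachment 11 describes its methods as general and leaves further detail to a Ventricular Repolarization Substudy Cardiac SAP; SAP Section 4.11.3 points to the same document.

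**The concern.** The rule looks only at the location of a maximum. It does not ask whether the maximum is large enough to be an effect, and it makes no allowance for sampling error. Some time point always has the largest mean. If there is no drug effect, that time is decided by noise, and most of the sampled times lie more than an hour from the end of infusion.

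The result the substudy hopes to show, no QT effect, is therefore the one most likely to be labelled a violation of a key model assumption. Further modelling would be started by noise, with little signal to support a delay parameter, and with no stated rule for which model supplies the predicted mean that is compared with 20 ms.

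**Working it through.** The documents state no error rate for this check, so there is no figure to reproduce. The 2% to 9% false-negative range cited under Sample Size Determination concerns concentration-QTc models and is a different quantity.

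**Inputs from the documents**
- Post-dose times: 0.5, 1, 2, 4, 6, 8 h (Attachment 11, Table 15).
- Infusion: 2 h, constant rate (Section 6).
- Evaluable subjects: about 30 active and 15 placebo (Attachment 11).
- Half-life: Attachment 11 says the PK data "consistently demonstrated a plasma half-life of approximately 4 to 5 hours and no plasma accumulation at later cycles".

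**Inputs inferred or assumed**
- tmax = 2 h, inferred from the infusion length and the end-of-infusion sample.
- SD of the change in QTcF and correlation between times: not in the documents. Ranges are shown.

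**Step 1. Times that pass.** The distances from 2 h are 1.5, 1, 0, 2, 4 and 6 h. Only 1 h and 2 h are within one hour.

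**Step 2. No QT effect.** With exchangeable errors each time is equally likely to hold the maximum, so P(flag) = 1 - 2/6 = 4/6 = 66.7%. Simulation with independent or equally correlated errors gives 66.6% to 66.7%. The figure does not depend on the SD or the sample size. If correlation decays with the time between ECGs it is 68% to 74%. If tmax is taken as just after 2.0 h, the 1-h time drops out and P(flag) = 5/6 = 83%.

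**Step 3. A direct (undelayed) effect.** The SE of each by-time mean is SD x sqrt(1/30 + 1/15) = 0.316 x SD. At half-life 4.5 h the relative concentrations at the six times are about 0.28, 0.54, 1, 0.73, 0.54 and 0.40. False flags by simulation:

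| Effect at Cmax | SD 7-10 ms, correlation 0.5-0.7 | SD 6-12 ms, independent errors, half-life 4-5 h |
|---|---|---|
| 0 ms | 67% | 67% |
| 5 ms | 25-43% | 36-54% |
| 10 ms | 6-23% | 15-41% |
| 20 ms | not run | 1-21% |

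**Step 4. Adding a 5-ms floor.** The rule now flags only if the maximum is at least 5 ms and also lies outside 1-2 h. With no effect and independent errors, P(flag) = (4/6) x [1 - Phi(5/SE)^6].
- SD 7 ms: SE = 2.21, 5/SE = 2.26, Phi = 0.988, so P = 0.667 x (1 - 0.930) = 5%.
- SD 10 ms: SE = 3.16, 5/SE = 1.58, Phi = 0.943, so P = 0.667 x (1 - 0.703) = 20%.

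With between-time correlation 0.5-0.7, simulation gives 3-14%.

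**Step 5. Does the floor still detect a real delay?** For an effect-compartment delay with true peak near 3.4 h (largest sampled mean at 4 h), SD 7-10 ms and correlation 0.5-0.7:

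| Delayed peak | Current rule flags | With 5-ms floor |
|---|---|---|
| 10 ms | 85-94% | 84-94% |
| 20 ms | 95-99% | 95-99% |

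For a 10-ms effect peaking later, at 6 h, detection with the floor lies towards the top of an overall 84-99% range.

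**The case against.** The strongest reply is that little follows from a false flag. A reader might infer that the linear analysis would be abandoned in two trials out of three. The documents do not support that. The trigger is a judgement that the assumption does not appear to hold, the response is that other models are explored, and nothing says the linear model is dropped. A high flag rate also applies only when the true effect is nil or small: in the correlated scenarios it is 25-43% at a direct 5 ms and 6-23% at 10 ms.

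A reader might also infer that the alternative models could not be estimated under no effect, or that the QT verdict would change. Neither is shown. A delay parameter would be poorly identified at zero slope, but that would be visible. For the verdict, at SD 10 ms a by-time upper 90% bound reaches 20 ms only if a mean exceeds 20 - 1.645 x 3.16 = 14.8 ms, which is 4.7 standard errors from zero. A drug with no effect would essentially always stay below 20 ms on by-time bounds.

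Finally, the Cardiac SAP may already contain a magnitude condition or say which model governs.

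These points limit the consequence and they stand. They do not remove the defect. The location-only rule is already written into the protocol, so a different rule in the Cardiac SAP would have to replace it or conflict with it. Nor does any available text say which model decides.

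**Conclusion.** The concern holds as a defect in a stated decision rule, and it should be corrected. With no QT effect the check wrongly flags hysteresis in about 67% of trials. That figure rests on tmax at 2 h (inferred) and on exchangeable errors; decaying correlation or a slightly later tmax makes it worse. The figures for non-null effects and for the floor also rest on an assumed SD, correlation and effect profile.

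The consequence is an avoidable ambiguity about which model supports the 20-ms criterion. It is not a demonstrated loss of the primary analysis or a demonstrated wrong QT conclusion.

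**What to change.** In Attachment 11, Statistical Methods:

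1. Keep the one-hour rule, but apply it only when the largest mean placebo-corrected change in QTcF is at least a prespecified size, for example 5 ms. Otherwise conclude that there is no evidence of hysteresis and retain the linear model.
2. State that the linear mixed-effects model remains the primary analysis. If the rule is triggered, report the effect-compartment or indirect-response model beside it, together with the by-time mean placebo-corrected changes and their 90% CIs.
3. Put the same text in the Cardiac SAP, and say whether tmax is taken at nominal or actual time.

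A confidence-interval condition is not advised, such as requiring the lower 90% bound of the difference between a late time and the end of infusion to exceed zero. For a delay peaking near 3.4 h it flags only 22-43% of 10-ms effects and 47-89% of 20-ms effects, against 84-94% and 95-99% with the floor alone.

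The cost is a few sentences, with no change to sample size, ECG schedule or subject procedures. The downside is small: a delayed effect below the floor would not trigger a model change, although the by-time means planned for the hysteresis plot would still show it. The floor does little for false flags when a direct effect of about 10 ms is present, because the maximum then nearly always exceeds 5 ms. Item 2 covers that case.

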| 1.1 | 23JUN2021 | 
 In Section 4.2, added more details in pretreatment Hb derivation. In Section 4.9, clarified the best 8-week (16-week) interval definition. Added End of Treatment visit in starting date of TI and transfusion reduction interval calculations. In Section 4.7, added 30 days to the last dose date in the definition of concomitant medication. In Section 4.2.3, added a scenario in the imputation rule when the onset of an AE is missing both day and month. |
| 1.2 | 13APR2021 | 
 Modified the Ventricular Repolarization (QTc) substudy in Part 2 to separate it from the main study per Protocol Amendment 7. |
| 1.3 | 24JUN2022 | 
 Clarified biomarker analysis sets definition. Separate PRO analysis from main study SAP to PRO SAP. Clarified a few subgroup factors and cutoff values in 4.9.1.4 Examination of Subgroups and added baseline platelet and neutrophils. Clarified section 4.9.1.4 to all subgroup factors will be based on values recorded on the eCRF. Clarified 4.9.3.1 Variables Definition for Progression Free Survival (PFS) and Time to progression to AML. Removed “manual absolute peripheral blast count” from section 4.10.3. |
| 2.0 | 15SEP2022 | 
 Removed PRO measures from secondary endpoints and sequential hypothesis testing per discussion with FDA. Consider PROs as exploratory endpoints that will be descriptively summarized. Clarified the timing of unblinding in Section 3.1. Add Added ALT or AST >3.0 x ULN WITH Bilirubin >2.0 x ULN as adverse event of interest in Section 4.10.2 per Protocol Amendment 6. Clarified Part 1 refers to Phase 2 part and Part 3 refers to Phase 3 part of the study throughout the document. |

Parexel International

Geron Corporation
63935937MDS3001

Statistical Analysis Plan

| | | |
|--|--|---|
| | | 
5. Clarified that the primary efficacy analysis is planned 12 months (and no longer 15 months) after the last subject is randomized in the main study of Part 2 per Protocol Amendment 7.6. Clarified the IRC responsibilities per IRC charter v2.0. |
|--|--|---|

LIST OF ABBREVIATIONS

| Abbreviation / Acronym | Definition / Expansion |
|-------------------------------|--|
| AE | adverse event |
| ALP | alkaline phosphatase |
| ALT | alanine aminotransferase |
| AML | acute myeloid leukemia |
| ANC | absolute neutrophil count |
| ANOVA | analysis of variance |
| AnS | anemia subscale |
| aPTT | activated partial thromboplastin time |
| AST | aspartate aminotransferase |
| ATC | Anatomical Therapeutic Chemical |
| AUC | area under the curve |
| BM | bone marrow |
| C1D1 | Cycle 1 Day 1 |
| CI | confidence interval |
| Cmax | maximum plasma concentration |
| CMH | Cochran-Mantel-Haenszel |
| CR | complete remission |
| CTCAE | Common Terminology Criteria for Adverse Events |
| DMC | Data Monitoring Committee |
| eCRF | electronic case report form |
| ECG | electrocardiogram |
| ECOG | Eastern Cooperative Oncology Group |
| EOT | end of treatment |
| EPO | erythropoietin |
| EQ-5D-5L | EuroQol-EQ-5D-5L |
| ER | exposure response |
| ESA | erythropoiesis-stimulating agent |

Parexel International

Geron Corporation
63935937MDS3001

Statistical Analysis Plan

| Abbreviation / Acronym | Definition / Expansion |
|-------------------------------|---|
| EWB | emotional well-being |
| FAB | French-American-British |
| FACT-An | Functional Assessment of Cancer Therapy - Anemia-Related Effects |
| FACT-An TOI | FACT-An Trial Outcome Index |
| FWB | functional well-being |
| Hb | hemoglobin |
| HEC | Hepatic Expert Committee |
| HI-E | hematologic improvement-erythroid |
| HI-N | hematologic improvement-neutrophil |
| HI-P | hematologic improvement-platelet |
| HMA | hypomethylating agent |
| hTERT | human telomerase reverse transcriptase |
| INR | international normalized ratio |
| IPSS | International Prognostic Scoring System |
| IPSS-R | Revised International Prognostic Scoring System |
| IRC | Independent Review Committee |
| ITT | intent to treat |
| IWG | International Working Group |
| IWRS | Interactive web response system |
| LFT | liver function test |
| MAR | missing at random |
| mCR | Marrow complete remission |
| MDS | myelodysplastic syndrome(s) |
| MedDRA | Medical Dictionary for Regulatory Activities |
| MID | Minimal important difference |
| MITT | Modified ITT |
| MMRM | mixed-effects model with repeated measures |
| Modified IWG 2006 | Proposed modification of IWG 2006 response criteria in myelodysplasia |

Parexel International

Geron Corporation
63935937MDS3001

Statistical Analysis Plan

| Abbreviation / Acronym | Definition / Expansion |
|-------------------------------|---|
| NCI | National Cancer Institute |
| OS | overall survival |
| PD | pharmacodynamic(s) |
| PFS | progression free survival |
| PGIC | Patient Global Impression of Change |
| PK | pharmacokinetic(s) |
| PP | Per Protocol |
| PR | partial remission |
| PRO | patient-reported outcome(s) |
| PT | preferred term |
| PWB | physical well-being |
| QTc | corrected QT interval |
| QUALMS | Quality of Life in Myelodysplasia Scale |
| QUALMS-BF | QUALMS Benefit Finding |
| QUALMS-E | QUALMS Emotional Burden |
| QUALMS-P | QUALMS Physical Burden |
| RBC | red blood cell |
| SAP | Statistical Analysis Plan |
| SAE | serious adverse event |
| SD | standard deviation |
| SI | System International |
| SOC | system organ class |
| SWB | social/family well-being |
| TA | telomerase activity |
| TEAE | Treatment-emergent AEs |
| TI | transfusion independence |
| TL | telomere length |
| ULN | upper limit of normal |
| WHO | World Health Organization |

1 INTRODUCTION

This study is designed to evaluate the efficacy and safety of imetelstat in transfusion-dependent subjects with low or intermediate-1 risk myelodysplastic syndrome (MDS) that is relapsed / refractory to erythropoiesis-stimulating agent (ESA) Treatment.

The purpose of the statistical analysis plan (SAP) is to lay out key elements including definitions and statistical methods for the planned analyses for the primary, secondary and exploratory endpoints. It describes the final reporting for study MDS3001 as per protocol amendment #7 dated as September 2, 2021. Safety data to be reviewed by the Data Monitoring Committee (DMC) periodically are specified in the DMC SAP, which is specifically prepared for DMC reviews.

2 STUDY OBJECTIVES

2.1 Primary Objective(s)

Part 1 (Phase 2): To evaluate the efficacy and safety of imetelstat in transfusion dependent subjects with low or intermediate-1 risk MDS that is relapsed/refractory to ESA treatment.

Part 2 (Phase 3): To compare the efficacy, in terms of red blood cell (RBC) transfusion independence (TI), of imetelstat to placebo in transfusion dependent subjects with low or intermediate-1 risk MDS that is relapsed/refractory to ESA treatment.

